**9 Which of the following is correct regarding the Patient Card:**

- A. Give the Patient Card to the patients and advise them to carry it until the last dose of isatuximab.
- B. Give the Patient Card to the patients and advise them to carry it at all time and until six months after the last dose of isatuximab.
- C. Blood test results on the Patient Card are only from after starting isatuximab treatment.

[Correct answer: B]

PI- List drop down

[DP:1]

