### **9.3.4 Behaviour with respect to the safety messages**

Prescribers:

- All patients should be blood typed and screened prior to start treatment with isatuximab.

- 
- Consider phenotyping prior to starting isatuximab treatment as per local practice.
  - If treatment with isatuximab has already started, inform the blood bank that the patient is receiving isatuximab.
  - In the event of a planned transfusion, notify blood transfusion centres about the risk of interference with indirect antiglobulin tests.
  - Verify standing orders for transfusions to determine if your patient received isatuximab within the last year.
  - Give the Patient Card to the patients and advise them to carry it at all time and until six months after the last dose of isatuximab. Provide patient's pre-isatuximab compatibility profile, if available, to the blood bank.
  - Ask your patient to tell their other healthcare professionals that they have received isatuximab, particularly before a transfusion, and to show them their Patient Card.

Non-prescribers:

- In case of urgent need for transfusion, non-cross matched ABO/RhD compatible RBC units can be administered as per local bank practices.
- The interference mitigation methods include treating reagent RBCs with DTT to disrupt isatuximab binding or other locally validated methods.
- Since the Kell Blood group system is also sensitive to DTT treatment, Kell-negative units should be supplied after ruling out or identifying alloantibodies using DTT-treated RBCs.

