## WARNING FOR HEALTHCARE PROFESSIONALS

### APPROPRIATE MEASURES TO MANAGE ISATUXIMAB INTERFERENCE AND AVOID POSSIBLE RESULTING ADVERSE CLINICAL CONSEQUENCES

- Conduct blood type and screen tests on your patient prior to the first infusion of isatuximab.
- Consider phenotyping prior to starting isatuximab treatment as per local practice.
- Give your patient the latest version of the **Patient Card**.
- If treatment with isatuximab has already started, inform the blood bank that the patient is receiving isatuximab.
- In the event of a planned transfusion, please notify blood transfusion centers about the risk of interference with indirect antiglobulin tests.
- There is currently no available information with regards to how long the interference with the indirect Coombs test may persist after the last infusion of isatuximab. Based on the half-life of isatuximab, it is anticipated that isatuximab mediated positive indirect Coombs test may persist for approximately **6 months** after the last infusion. Therefore, please advise your patient to carry the Patient Card at all times and until 6 months after the last dose of isatuximab.
- It is important you always advise your patient to consult the Package Leaflet (PL) for further information on isatuximab.

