**Knowledge questions: Q2-Q3**

- 2 **Select true or false for the following statement on isatuximab:**  
*“Isatuximab is associated with risk of interference with blood compatibility tests”\**
  - True
  - False

[Correct answer: True]

PI- List drop down

\*Key safety question

[DP:1]

- 3 **Approximately how long may the isatuximab interference with indirect antiglobulin tests persist after the last infusion of isatuximab?**
  - A. One month
  - B. Three months
  - C. Six months
  - D. One year

[Correct answer: C]

---

PI- List drop down

[DP:1]

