**Behavior questions: Q4-Q10**

**4 Which of the following is correct regarding blood typing and screening?**

- A. Patients should not be blood typed and screened prior to start treatment with isatuximab
- B. Only select patients should be blood typed and screened prior to start treatment with isatuximab
- C. All patients should be blood typed and screened prior to start treatment with isatuximab

[Correct answer: C]

PI- List drop down

[DP:1]

-----Page Break-----

**5 Select true or false for the following statement: “*You should consider phenotyping prior to starting isatuximab treatment, as per local practice*”**

- True
- False

[Correct answer: True]

PI- List drop down

[DP:1]

**6 Select true or false for the following statement: “*If treatment with isatuximab has already started, there is no need to inform the blood bank that the patient is receiving isatuximab*”**

- True
- False

[Correct answer: False]

PI- List drop down

[DP:1]

**7 Select true or false for the following statement regarding the recommended measures of isatuximab treatment: “*In the event of a planned transfusion, notify blood transfusion centre about the risk of interference with indirect antiglobulin tests.*”**

- True
- False

[Correct answer: True]

PI- List drop down

[DP:1]

-----Page Break-----

**8 Select true or false for the following statement regarding the recommended measures of isatuximab treatment: “For timely transfusions, verify standing orders for transfusions to determine if your patient received isatuximab within the last year”**

- True
- False

[Correct answer: True]

PI- List drop down

[DP:1]

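### Q9 cannot tell six months from any other post-dose carrying period, so it and criterion 2 can overstate uptake of the Patient Card message

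*Protocol*

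**What the plan says.** Section 9.3.4 includes, among the seven prescriber behaviours, giving the Patient Card and telling patients to "advise them to carry it at all time and until six months after the last dose of isatuximab". In Appendix C the prescriber items are split into "Knowledge questions: Q2-Q3" and "Behavior questions: Q4-Q10".

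- **Q9** (behaviour) is the item for the Patient Card message. Option A is to "advise them to carry it until the last dose of isatuximab". Option B, the key, begins "Give the Patient Card to the patients and advise them to carry it at all time and until six months after the last dose of" (the drug name follows). Option C is a statement about which blood results appear on the card.
- **Q3** (knowledge) asks "Approximately how long may the isatuximab interference with indirect antiglobulin tests persist after the last infusion of isatuximab". It offers one month, three months, six months and one year, and is keyed to six months.
- **Q8** (behaviour) is true/false on whether, for timely transfusions, one should "verify standing orders for transfusions to determine if your patient received isatuximab within the last year". It is keyed True.

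Section 9.7.4 sets the success rule at 80% of HCPs on three criteria: the first knowledge question (Q2), at least five of seven behaviour items for prescribers (criterion 2), and at least two of three for non-prescribers. It names no key item among the behaviour questions. It also plans the proportion correct for every question.

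The brochure (Appendix A) gives about six months for the interference and for carrying the card, and a one-year look-back for standing transfusion orders. It also states: "There is currently no available information with regards to how long the interference with the indirect Coombs test may persist after the last infusion".

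**The concern.** A multiple-choice item measures only what its wrong options can separate. Q9 states a six-month period, but no wrong option offers a different period after the last dose. A correct answer shows that the prescriber does not think carrying ends at the last dose. It does not show that the prescriber knows the period.

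Section 7 lists the length of interference among the messages aimed at prescribers, and section 9.3.4 puts the carrying period among the behaviours to be measured. The one item that discriminates between durations, Q3, is in none of the three criteria. The effectiveness verdict therefore credits uptake of this message through an item that does not test its figure. Once the survey is fielded, Q9 answers cannot be rescored for duration.

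A second, smaller matter is that the materials use two windows, six months and one year, for different purposes and do not say why they differ. Both appear as scored content, in Q3 and Q8.

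**Working it through.** **1. What Q9 separates.** Set each belief about carrying the card against the options:

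| Belief about carrying after last dose | Option chosen | Scored |
|---|---|---|
| Ends at last dose | A | wrong |
| One month | B, by elimination | correct |
| Three months | B, by elimination | correct |
| Six months | B | correct |
| One year | B, by elimination | correct |

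Let *a* be the share holding six months, *b* the share holding another non-zero period, and *c* the share holding that carrying ends at the last dose. The expected Q9 score is *a* + *b*. Uptake of the message is *a*. The overstatement is *b*, for which the protocol gives no value.

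**2. Effect on criterion 2.** The plan's only figure here is the pass mark, 5/7 = 71.4%. Assume independent items, with probability p on each of the other six and q on Q9:

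P(pass) = q × P(Bin(6, p) ≥ 4) + (1 − q) × P(Bin(6, p) ≥ 5)

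The values of p are assumptions. At p = 0.80 and q = 1/3: (1/3)(0.9011) + (2/3)(0.6554) = 0.737.

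| p | Q9 by elimination (q = 1) | Q9 guessed, three options (q = 1/3) | Q9 guessed, four periods (q = 1/4) | Q9 wrong (q = 0) |
|---|---|---|---|---|
| 0.80 | 0.901 | 0.737 | 0.717 | 0.655 |
| 0.90 | 0.984 | 0.919 | 0.910 | 0.886 |
| 0.95 | 0.998 | 0.977 | 0.975 | 0.967 |
| 1.00 | 1.000 | 1.000 | 1.000 | 1.000 |

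For a prescriber in group *b*, the present Q9 raises the chance of passing by 0.901 − 0.655 = 0.246 at p = 0.80, 0.984 − 0.886 = 0.098 at p = 0.90, and 0.998 − 0.967 = 0.031 at p = 0.95. The prescriber pass rate rises by *b* times that difference.

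**3. What a better Q9 would not do.** A prescriber who misses Q9 and has everything else right scores 6 of 7 and passes. One who misses Q8 and Q9 scores 5 of 7 and also passes. This follows from the 5-of-7 rule and would remain after Q9 is mended.

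**4. The two windows.** Suppose a prescriber reasons from six months, answers Q8 False and loses that item. The remaining task is 5 of 6. With p on every other item:

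| p | P(≥ 5 of 7) | P(≥ 5 of 6) | Share losing Q8 that brings the group to 80% |
|---|---|---|---|
| 0.80 | 0.8520 | 0.6554 | (0.8520 − 0.80)/(0.8520 − 0.6554) = 0.26 |
| 0.85 | 0.9262 | 0.7765 | (0.9262 − 0.80)/(0.9262 − 0.7765) = 0.84 |
| 0.90 | 0.9743 | 0.8857 | not reached; 0.8857 exceeds 0.80 |

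The break-even share runs from about a quarter to unreachable over a narrow range of p, so it supports no firm statement about the verdict.

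**The case against.** The best defence is that duration is tested properly elsewhere. Q3 has four distinct periods and its result is reported on its own, so poor knowledge of six months would be visible in the report. Keeping Q3 out of the success rule is a declared choice: section 9.7.4 explains why the overarching message carries the weight and why no behaviour item is singled out. This stands, and it limits the severity. It does not mend Q9, which is scored as evidence of the carrying period.

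Three stronger readings are tempting, and the documents do not support them.

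- *Q3 and Q8 are scored inconsistently.* They ask different things: how long interference may last, and how far back to check standing orders. Both keys follow the brochure and both can be true, since a one-year look-back contains the six-month period. Q8 already repeats the brochure's wording closely. That a prescriber would infer False from six months is conjecture.
- *Q9 detects no wrong duration.* Option A is a wrong duration, zero months after the last dose, and it is marked wrong.
- *Criterion 2 can be met without the six-month message because of these items.* The cause is the tolerance of any two misses. The same is true of every other single behaviour message.

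**Conclusion.** The point holds as an item-design fault with a limited reach. Q9 detects only the belief that carrying ends at the last dose. Its score overstates uptake of the six-month message by the share holding another non-zero period, and criterion 2 inherits part of that. The gain per such prescriber runs from 0.246 at p = 0.80 to 0.031 at p = 0.95 and nil at p = 1, assuming independent items and elimination on Q9. Neither p nor the share is given in the protocol, so the effect on the group pass rate cannot be fixed.

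The six-month and one-year windows are unexplained rather than shown to conflict. The passages should be reconciled or the difference explained; no view is taken here on which is right. Any effect through Q8 depends wholly on the assumed p.

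**What to change.** 1. Before translation and the pilot interviews in section 9.4, reword Q9 so that its options contain more than one non-zero carrying period, keyed to the figure in the materials. Settle the alternatives after step 3: using one year as a wrong option would bring the unexplained window into a criterion 2 item. Q3 can stay as it is.
2. Report the Q3 and Q9 proportions side by side with criterion 2, so that the verdict is read with the duration result next to it.
3. Reconcile the six-month and one-year statements in the brochure, section 9.3.4, Q3 and Q8, or state why they differ.

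Steps 1 and 2 cost one reworded item, its translations and one table. They need no extra respondents. Q9 becomes harder, so the prescriber pass rate may be slightly lower. They do not guarantee knowledge of the duration, because 5 of 7 has no mandatory item. For step 3, an explanation in the protocol is cheap. A change to the brochure is not, because Table 1 shows it already distributed in most of the listed countries, several with a completed revised version.

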**10 You should advise your patients:**

- A. To not tell their other healthcare professionals they have received isatuximab after a transfusion
- B. That they do not need to show other healthcare professionals their Patient Card during a transfusion

C. To tell their other healthcare professionals they have received isatuximab, particularly before a transfusion and to show them their Patient Card

D. None of the above

[Correct answer: C]

PI- List drop down

[DP:1]

-----Page Break-----

---

## Questions for Non-prescribers

“Provided blood products on a regular basis” or “at least once” on question Px2.

**1 Have you received the educational material from Sanofi regarding the minimization of a risk associated with isatuximab?**

- Yes
- No

PI- List drop down

[DP:1]

### Knowledge questions: Q2-Q4

**2 Select true or false for the following statement on isatuximab:**

***“Isatuximab is associated with risk of interference with blood compatibility tests”\****

- True
- False

[Correct answer: True]

PI- List drop down

\*Key safety question

[DP:1]

**3 Which of the following is correct regarding isatuximab interference?**

- A. Isatuximab binds to CD20 on RBCs
- B. Isatuximab binds to CD38 and may interfere with routine blood compatibility tests with potential false positive reactions in Indirect Antiglobulin Test (Indirect Coombs Test)
- C. Isatuximab does not mask the detection of antibodies to minor antigens in the patient’s serum

[Correct answer: B]

PI- List drop down

[DP:1]

-----Page Break-----

**4 Isatuximab interferes with:**

- A. ABO typing
- B. Rh typing
- C. Indirect Antiglobulin Test (Indirect Coombs Test)
- D. None of the above

[Correct answer: C]

PI- List drop down

[DP:1]

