## **9 Research Methods**

### **9.1 Study Design**

This is a non-interventional cross-sectional study among HCPs involved in the treatment of MM with SARCLISA (isatuximab) in selected European countries.

The study is a cross-sectional survey planned to be conducted within 12-18 months after implementation of educational materials in each country. The surveys will be conducted online, using structured questionnaires, comprising close-ended questions where the response format is either the selection of a single response or selection of a number of responses as appropriate. Information will be collected from HCPs using the online LiveTracker™ platform. LiveTracker™ is a cloud-based, real-time, continuous electronic data collection platform tracker that delivers real-world evidence data.

This PASS will be conducted according to the Guideline on good pharmacovigilance practices (GVP) – Module VIII (Rev 3) dated 9 October 2017 (7) and according to the GVP Module XVI (Rev 2) dated 28 March 2017 (EMA/204715/2012 Rev 2).

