### **9.3.3 Knowledge of each safety messages**

Key safety message for All HCPs:

- Isatuximab is associated with risk of interference with blood compatibility tests

Prescribers:

- There is currently no available information on how long the interference may persist after the last infusion of isatuximab. Based on the half-life of isatuximab, the interference with indirect antiglobulin tests may persist for approximately six months after the last infusion.

Non-prescribers:

- Isatuximab bound to CD38 on RBCs and may mask the detection of antibodies to minor antigens in the patient's serum. Isatuximab may interfere with routine blood compatibility tests with potential false positive reactions in IAT.
- The determination of a patient's ABO and Rh blood type are not impacted

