## WARNING FOR BLOOD BANKS

- Isatuximab is bound to CD38 on red blood cells (RBCs) and may mask the detection of antibodies to minor antigens in the patient's serum. Thus, isatuximab may interfere with routine blood compatibility tests with **potential false positive reactions in indirect antiglobulin tests (indirect Coombs tests)**.
- This interference is limited to the minor blood groups and does not affect the determination of a patient's ABO and Rh blood type.
- Isatuximab interference mitigation methods include treating reagent RBCs with dithiothreitol (DTT) to disrupt isatuximab binding or other locally validated methods. Since the Kell Blood group system is also sensitive to DTT treatment, Kell-negative units should be supplied after ruling out or identifying alloantibodies using DTT-treated RBCs.
- If an emergency transfusion is required, you can give non-cross-matched ABO/Rh-compatible RBCs as per local blood bank practices.

ISA = Isatuximab    Y = Coombs reagent    ● = CD38 receptor    ● = Red Blood Cells    Y = Antibodies to minor antigen

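### Non-prescriber Q4, the only item on ABO and Rh typing, measures that message incompletely: a respondent who wrongly believes typing is affected can still score correct

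*Protocol*

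**What the plan says.** Protocol section 9.3.3 lists three knowledge messages for non-prescribers: the key message shared with prescribers, the mechanism with its false positives in the indirect antiglobulin test, and, separately, "The determination of a patient's ABO and Rh blood type are not impacted". The brochure in Appendix A gives the last one its own bullet: "This interference is limited to the minor blood groups and does not affect the determination of a patient's ABO and Rh blood type".

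Appendix C tests non-prescriber knowledge with Q2 to Q4. Q2 is the key question. Q3 covers CD38, masking and the antiglobulin test. Q4, "Isatuximab interferes with", offers ABO typing, Rh typing, the indirect antiglobulin test and a none option. Its programming note is "PI- List drop down" and its key is "Correct answer: C", the antiglobulin test.

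Section 9.1 allows both formats: "the response format is either the selection of a single response or selection of a number of responses as appropriate". Nothing in Appendix C marks Q4 as a multiple-selection item.

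Section 9.7.4 reports the proportion correct for each question. It also reports the proportion of HCPs with 70%, 80%, 90% and 100% of answers correct, for all questions, for knowledge questions and for behaviour questions.

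**The concern.** The misconception that this message is meant to prevent is that interference extends beyond the antiglobulin test to ABO or Rh typing. Someone with that misconception may well also know that the antiglobulin test is affected. With one answer allowed, that person cannot report both beliefs, and choosing the antiglobulin test earns a correct score.

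The Q4 percentage will naturally be read as the share of blood-bank and transfusion staff who know that ABO and Rh typing are unaffected, which is one of the three knowledge results under objective 2 for this group. If it includes people who believe the opposite, the report overstates how well the message was taken in. No later analysis can separate them, because the second belief is never recorded.

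**Working it through.** The plan gives no figure on this point, so there is none to reproduce. The check has three parts.

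**1. Which items bear on the message**

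- Q2 asks only whether there is a risk of interference with compatibility tests.
- Q3 does not mention ABO or Rh. Its keyed option reads "Isatuximab binds to CD38 and may interfere with routine blood compatibility tests with potential false positive reactions in Indirect Antiglobulin Test" and stands on the page before Q4, so it may cue the keyed answer there.
- Q5 mentions ABO/RhD-compatible units, but asks whether they may be issued in an emergency, not whether typing is affected.
- Q4 is the only item that offers ABO or Rh typing as something that might be affected.

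**2. How Q4 scores each belief** (yardstick: the respondent believes the antiglobulin test is affected and ABO/Rh typing is not)

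| Belief about what is affected | Answer available | Score | Score matches belief? |
|---|---|---|---|
| Antiglobulin test only | C | correct | yes |
| ABO or Rh typing, not the antiglobulin test | A or B | wrong | yes |
| Both, picks A or B | A or B | wrong | yes |
| Both, picks C | C | correct | **no** |
| Nothing | D | wrong | yes |

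The only mismatch is in the fourth row, and it runs upward.

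**3. Size, under assumed inputs**

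The documents give none of the following three inputs:

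- k = share who know the antiglobulin test is affected = 0.80
- s = share of those who also believe ABO/Rh typing is affected = 0.10 to 0.30
- q = probability that such a respondent chooses C = 1/3 (indifferent among A, B and C) to 1

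True share = k(1 - s). Q4 score = k(1 - s) + k·s·q. Overstatement = k·s·q.

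| s | q | True share | Q4 shows | Overstatement |
|---|---|---|---|---|
| 0.10 | 1/3 | 72% | 74.7% | 2.7 points |
| 0.10 | 1 | 72% | 80% | 8 points |
| 0.30 | 1/3 | 56% | 64% | 8 points |
| 0.30 | 1 | 56% | 80% | 24 points |

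Table 3 targets 40 to 100 non-prescribers. With p = 0.80 and an assumed 95% level, the sampling half-width is 1.96·√(0.16/40) = 12.4 points at 40 and 1.96·√(0.16/100) = 7.8 points at 100. The bias is smaller than this at the low end of the range and larger at the high end.

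**Effect on the summaries** (reading each threshold as at least that percentage)

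- Knowledge questions: three items give scores of 0, 33, 67 or 100%. All four thresholds need 3/3, so one falsely correct Q4 moves an HCP who has Q2 and Q3 right from failing all four to passing all four.
- All questions: six scored items (Q2 to Q7). 4/6 = 67% and 5/6 = 83%, so 70% and 80% need 5/6, while 90% and 100% need 6/6. Q4 can decide any of these.
- Satisfactory criterion in section 9.7.4: the key question (Q2) and at least two of three behaviour questions (Q5 to Q7). Q4 does not enter.

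**The case against.** The strongest reply is that Q4 does test the message. ABO and Rh typing are two of its four options and choosing either is marked wrong, so the misconception is caught whenever it displaces the antiglobulin test. This stands. A reader might infer that the message is not measured at all; the answer key does not support that.

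A reader might also infer that everyone who holds both beliefs is scored correct, which gives 8 to 24 points. Nothing in the documents says that such a respondent always picks C, and options A and B are listed first. That figure is the q = 1 case only.

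Nor does Q4 merely repeat Q3. Q3 tests target, masking and false positives, while Q4 asks which test is affected. Q3's keyed option is shown as one of three unmarked statements, so any cueing is possible but of unknown size.

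Two further replies carry less weight. Single choice is not printed at Q4; it is inferred from the drop-down, the one keyed letter, the none option and the lack of a select-all instruction. Section 9.1 would permit multiple selection, but nothing assigns it here. Section 9.4 plans user acceptance testing and pilot interviews with two HCPs per country, which might expose the problem but cannot be relied on to do so.

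Finally, the item agrees with the brochure and its format is permitted, so the protocol does not contradict itself. That is true. The weakness is in what a correct answer can show.

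**Conclusion.** The point holds as one of incomplete measurement. A correct Q4 shows that the respondent puts the antiglobulin test first among the options. It does not show that the respondent knows ABO and Rh typing are unaffected. Among respondents who hold both beliefs, any scoring error is upward. Its size is about 3 to 24 points under the stated assumptions on k, s and q. The defect itself follows from the item's construction and does not depend on those values.

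It reaches the Q4 percentage and the knowledge and all-question summaries for non-prescribers. A reader might infer that the study's conclusion on effectiveness is at risk. The documents do not support that: Q4 lies outside the 80% satisfactory criterion, and section 9.7.4 gives the key question more weight than all others. The change is worth making because the questionnaire is fixed in Appendix C and the lost information cannot be recovered after fieldwork.

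**What to change.** Before fieldwork, do one of the following:

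- Make Q4 a select-all item with the same options, the none option excluding the others, scored correct only if the indirect antiglobulin test alone is ticked. Section 9.1 already allows this format.
- Replace Q4 with a direct true/false statement that isatuximab affects the determination of ABO and Rh blood type, keyed False. Q3 still covers the antiglobulin test.

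The first is preferable, because it records which misconception is held and is harder to guess than a true/false item. Either costs one change in programming and translation. The sample size and the satisfactory criterion stay as they are. The reported percentage will probably be lower.
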